Cognitive behavioral therapy (CBT) is considered the gold-standard of empirically-based psychosocial treatments for depression (Cuijpers et al., 2013). Thus, CBT may serve as a useful, standardized foundation of psychosocial treatment to provide for patients with depression who are receiving psilocybin treatment. Additionally, psilocybin may help facilitate the uptake of CBT skills. Since psilocybin engenders greater cognitive flexibility and behavioral motivation (e.g., greater openness and social connectedness), it may help facilitate the uptake of CBT skills. Depressed individuals’ negative beliefs and unhelpful behaviors can become quite fixed, which can make treatment progress slow. Together, psilocybin may be a helpful catalyst for the cognitive and behavioral changes that are sought in CBT, and CBT may help to solidify cognitive and behavioral changes that are spurred by the psilocybin experience.

This study seeks to build on the current approaches to psilocybin treatment by combining CBT with the already-established psilocybin + PAT approach to (1) test whether CBT can be feasibly and acceptably added to the current psilocybin treatment modality and (2) to work towards protocolizing the psychosocial treatment that adjoins psilocybin drug therapy.

GENERAL INVESTIGATIONAL PLAN:

This study is a preliminary, proof-of-concept pilot to determine feasibility of the treatment methods and effect sizes. The study design is a single-group, fixed dose trial whereby 30 eligible participants will undergo 12 sessions of CBT during which two doses of psilocybin will be administered— a 10mg dose following the third session and a 25mg dose following the sixth session. Participants will be followed for an additional 3 months following treatment

termination. Study procedures will follow previously established safety guidelines (Johnson et al., 2008).

We hypothesize that psilocybin as an adjunct to 12 sessions of CBT will:

- (1) be feasible and reviewed favorably by participants, with minimal to no adverse effects;
- (2) Lead to reductions in negative thinking, increases in engagement with the environment, and improvements in depressive symptoms over the 7-month study period.

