PRIMARY OUTCOME MEASURES AND STATISTICAL ANALYSIS PLAN:

The study's primary assessments will be held prior to starting the CBT (i.e., baseline), within two weeks following the CBT's completion, and three months following the treatment's completion. Secondary measurements will also be collected immediately following each drug session. The study will terminate following the three-month follow-up assessment. A schematic of the study design is presented in Figure 1 below.

To determine feasibility, we will track the number of participants engaged at each phase of screening (i.e., phone screen, physical screen, and psychological screen), the number consented and enrolled, and the number who completed the 4-month treatment. Acceptability was measured by participants at the post-treatment assessment using the Client Satisfaction Questionnaire 8 (CSQ-8; Larsen et al., 1979). Participants' and clinicians' quantitative and qualitative feedback will be collected, using an internally-created questionnaire containing 5-point scales of helpfulness. Depressive symptom severity over the previous 1-2 weeks will be assessed using the 17-item Hamilton Depression Rating Scale (HAM-D; Hamilton, 1986). Psychosocial functioning over the two weeks prior to the assessment will be rated by a study assessor assessed using the 100-point Global Assessment of Functioning Scale (GAF; American Psychiatric Association, 2000).

Feasibility metrics will be tabulated by calculating percentages of participants enrolled and retained through the treatment divided by the total number of participants consented and screened. Acceptability metrics will be calculated based on the participant-rated CSQ-8. We will calculate the mean and standard deviation. We will examine within-subjects changes in depressive symptoms (HAM-D) and functioning (GAF) using repeated measures analyses of variance (ANOVA) in IBM's SPSS version 30.0. Time will be the independent fixed factor variable, based on the interval assessments of the study (baseline, post-treatment, follow-up).

Figure 1. Study Design Schematic for Eligible Participants

STUDY DRUGS:

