Participant Monitoring and Removal from the Study:

Noncompliance. Participants will be withdrawn from the protocol if they are noncompliant with the study procedures (for example, missing 2 or more consecutive CBT without calling ahead; refuse to participate in follow-up interviews).

Failing the medical or psychological screening. Participants will be withdrawn from the study if any of the following are evidenced during the medical screen or psychological screen, or if any of the following are elucidated during study:

- A personal or family history (first or second-degree) of psychosis or bipolar disorder
- Resting blood pressure above 140 systolic, 90 diastolic or heart rate > 90 beats per minute (averaged across four separate measurements)

- Meeting criteria for a DSM-5 cluster B personality disorder (narcissistic, histrionic, borderline, antisocial personality disorder),
- Active suicidality (i.e., HAM-D item 3 score of 3 or greater) or other psychiatric disturbance requiring acute treatment
- Current use of antidepressants, other serotonergic-affecting substances (e.g., St. John's Wort and 5-hydroxytryptophan), lithium, or efavirenz [regardless of whether the drug(s) is/are prescribed for MDD or other conditions]
- Current use of opioids (e.g., codeine, fentanyl, hydrocodone, meperidine, tramadol)
- Currently receiving cognitive behavioral therapy,
- Any of the following cardiovascular conditions: uncontrolled hypertension, coronary artery disease, congenital long QT syndrome, cardiac hypertrophy, cardiac ischemia, congestive heart failure, myocardial infarction, tachycardia, artificial heart valve, a clinically significant screening ECG abnormality, or any other significant cardiovascular condition
- QTc interval measurement of > 450 ms in males or > 460 ms in females as measured by the baseline ECG
- A history of stroke or Transient Ischemic Attack (TIA)
- Epilepsy or history of seizures
- Insulin-dependent diabetes
- Meeting criteria for a DSM-5 substance abuse or dependence within prior 6 months (including for nicotine and cannabis)
- Positive urine drug screen for illicit substances (excluding cannabis)
- Use of other psychedelics or ketamine within prior 12 months
- Adverse prior reaction to a psychedelic agent
- Pregnant, trying to get pregnant, or nursing

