Any participant who is withdrawn from the study for any of the above exclusionary criteria will be referred to treatment elsewhere. For participants who have begun CBT, they will be retained in the study protocol (but not allowed to participate in forthcoming psilocybin sessions) for as long as possible, or until the CBT has ended.

Adverse drug reaction. Participants will be withdrawn from the study if they have an overwhelmingly distressing response to the first, low dose drug session. An overwhelmingly distressing response is considered one that requires hospitalization due to acute unmanageable psychosis, psychological distress, or a hypertensive crisis (i.e., blood pressure at or exceeding 180 systolic and 120 diastolic mmHg); use of rescue medication due to acute psychosis, psychological distress/anxiety, or elevated blood pressure (i.e., blood pressure exceeding 160 systolic and 100 diastolic mmHg); or otherwise is determined by study staff that the participant cannot be kept safe on a higher dose of the drug. Additionally, participants will be withdrawn from the study if they have an allergic reaction (e.g., swelling, itching) caused by the psilocybin or any persisting headaches or visual-perceptual effects that are distressing or interfering and lasting longer than two days after the first psilocybin administration. The participant will be referred to treatment elsewhere but will be retained in the study protocol for as long as possible or until the CBT has ended. Any participant with an adverse drug reaction to the second psilocybin administration will be offered continued support via the study's outlined CBT protocol.

These circumstances that may require administrative withdrawal will be spelled out in the consent

forms. Despite being withdrawn from study interventions, we will attempt to retain these participants for study assessments with their consent.

Participant worsening or non-response

Each participant will be seen weekly by their study therapist for two months following their first psilocybin session and one month following their second psilocybin session. Participants will continue to engage in biweekly therapy for the next month. Participants will then undergo a study assessment within two weeks of their treatment termination and another three months following treatment termination. At each of these visits, subjects' depressive symptoms (including suicidality) and functioning will be monitored.

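### The repeated-measures ANOVA has no missing-data rule and, as usually run, rests on participants with all three scores; use an all-available-data mixed model plus a sensitivity analysis for informative loss

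*Combined protocol and SAP*

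**What the plan says.** The section on primary outcome measures and statistical analysis gives the efficacy analysis in two sentences. The study will examine "within-subjects changes in depressive symptoms (HAM-D) and functioning (GAF) using repeated measures analyses of variance (ANOVA", "in IBM's SPSS version 30.0". The model has one factor: "Time will be the independent fixed factor variable, based on the interval assessments of the study (baseline, post-treatment, follow-up". The two later visits fall "within two weeks following the CBT's completion, and three months following the treatment's completion".

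The General Investigational Plan describes a "single-group, fixed dose trial whereby 30 eligible participants will undergo 12 sessions of CBT", and calls it a "preliminary, proof-of-concept pilot to determine feasibility of the treatment methods and effect sizes".

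No section defines an analysis population, a rule for missing HAM-D or GAF scores, an imputation method or a sensitivity analysis. The SPSS procedure is not named. No confidence interval or effect-size measure is specified.

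On loss of participants, the documents point both ways:

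- **Routes out.** The removal rules under Adequacy of Protection Against Risks take participants out when their physical or mental state is seen to decline. The noncompliance rule under Safety Measures gives as examples "missing 2 or more consecutive CBT without calling ahead; refuse to participate in follow-up interviews".
- **Efforts to keep assessing.** The passage on adverse drug reactions says that after withdrawal from the interventions "we will attempt to retain these participants for study assessments with their consent". The passage on worsening or non-response keeps worsening participants in CBT and assessments as far as can be managed.

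**The concern.** A conventional repeated-measures ANOVA, such as SPSS GLM Repeated Measures, needs a complete row for each participant. Someone with baseline and post-treatment scores who misses the 3-month visit contributes nothing, even to the baseline-to-post-treatment comparison for which both scores exist. The effort to keep assessing withdrawn participants is then partly wasted: a score collected from someone who still misses one visit is not used.

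If those who miss a visit improved less than the others, the completer mean overstates improvement. Two removal routes can be related to outcome: observed decline, and refusal of follow-up. There is no control arm in which a similar bias might partly cancel. A pilot meant to supply effect sizes would then pass an inflated one to the design of the next trial.

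Separately, an F-test on a three-level Time factor does not itself give the size of change with its uncertainty.

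**Working it through.** **1. The plan's own figure.** There is nothing to reproduce. The sample size of 30 comes with no alpha, power, effect size, standard deviation or dropout rate. All inputs below other than n = 30 and the three visits are assumptions.

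**2. How many participants remain.** Let d be the proportion lost. If both later visits are lost together, completers = 30 × (1 − d). If each later visit is missed independently with probability d, completers = 30 × (1 − d)².

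| d | Lost together | Missed independently |
|---|---|---|
| 10% | 27 | 24.3 |
| 20% | 24 | 19.2 |
| 30% | 21 | 14.7 |

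**3. Direction and scale of the bias.** The overall mean improvement is (1 − d) × completers' mean + d × mean of those dropped. Hence

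completer mean − overall mean = d × (completers' mean − mean of those dropped).

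With a 4-point HAM-D gap this is 0.4, 0.8 and 1.2 points at d = 10%, 20% and 30%. With a 6-point gap it is 0.6, 1.2 and 1.8. A 10-point gap would give 1.0, 2.0 and 3.0, but at 30% loss that is a wider gap than the simulations below produce. The sign is fixed whenever those dropped improved less.

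**4. Loss that depends on an observed score.** Assumptions: n = 30; baseline HAM-D mean 21 (SD 4); true change −10 at both later visits (SD 7); correlation 0.3 between baseline and later scores and 0.5 between the two later scores; 10% lost at random before post-treatment. Further loss before follow-up has odds that rise with the post-treatment HAM-D (logistic slope per point). There were 4,000 simulated trials per scenario.

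| Later loss and slope | Completer overstatement, post-treatment | Completer overstatement, follow-up | Likelihood estimate on all scores, post-treatment |
|---|---|---|---|
| 10–20% at 0.05, or 10% at 0.15 | 0.2 to 0.6 | below 0.4 | about −10.0 |
| 20–30% at 0.15 to 0.25 | 1.1 to 2.1 (change −11.1 to −12.1, on 19–22 people) | 0.4 to 0.8 | about −10.0 |

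The steeper slopes are strong assumptions. Per SD of 7 points, the odds of loss multiply by exp(0.15 × 7) = 2.9 to exp(0.25 × 7) = 5.8.

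**5. Random loss.** The SD of the baseline-to-post-treatment change is √(16 + 49 − 2 × 0.3 × 4 × 7) = √48.2 = 6.94. After 10% early loss, 27 people have both scores: SE = 6.94/√27 = 1.34, and the 95% half-width is about 2.7. If a further 25% are lost and deleted, 27 × 0.75 = 20.25 remain: SE = 6.94/√20.25 = 1.54, and the half-width is about 3.2. There is no bias.

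**6. Loss that depends on an unseen score.** In the step 4 set-up, letting the early 10% loss also depend on the unobserved post-treatment score moves the likelihood estimate to about −10.6 to −10.9, against a true −10.

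A second set of assumptions shows the same limit: HAM-D means 22, 12 and 13; SDs 4, 6 and 6; correlations 0.3, 0.3 and 0.7; non-responders four times as likely to be lost. True post-treatment improvement is 10 points.

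| Loss | Completers, follow-up visit only lost | Likelihood, follow-up visit only lost | Completers, both later visits lost | Likelihood, both later visits lost |
|---|---|---|---|---|
| 10% | 10.3 | 10.0 | 10.3 | 10.3 |
| 20% | 10.6 | 10.0 | 10.6 | 10.6 |
| 30% | 11.1 | 10.0 | 11.1 | 11.1 |

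The mixed model removes the bias when the loss depends on scores already recorded. It removes none when non-responders are seen only at baseline.

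**The case against.** - **The plan does not say that anyone will be dropped.** Correct. It names neither the SPSS procedure nor a deletion rule, and the MIXED procedure in the same package would keep partial data. A reader might infer that the sponsor has committed to a completer analysis. The documents support only that the usual form of the named method works that way and that nothing written prevents it.
- **The protocol works to limit loss.** This stands in large part. Many withdrawals stop dosing, not assessment. But continued assessment is an attempt that depends on consent, the decline and noncompliance rules still allow loss, and none of this says how a missing score is analysed. Nor does it follow that the data of withdrawn participants in general are discarded; that applies only to those who still miss a visit.
- **The larger figures need steep dropout.** Also fair. Under milder loss the bias is 0.2 to 0.6 points, well inside the sampling SD of about 1.4 points for the completer estimate. No input comes from the documents.
- **Feasibility comes first, and no confirmatory decision rests on the F-test.** True, and the feasibility percentages and satisfaction scores are untouched. This lowers the severity, but effect size is also a stated purpose.
- **Confidence intervals can accompany an ANOVA.** They can, but the plan commits to none.

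**Conclusion.** The point holds in a limited form. The plan names a method that ordinarily uses only participants with complete data, has no missing-data rule, and leaves a single-arm pilot open to overstating improvement if those who miss a visit did worse. Under assumed later loss of 10–30% related to the post-treatment HAM-D, the overstatement is about 0.2 to 2 points at post-treatment and less than 1 point at follow-up. Under random loss the cost is precision alone.

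The direction follows algebraically from the condition that those lost improved less. The size rests wholly on assumed dropout, means, SDs and correlations.

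A reader might go further and conclude that the trial's result will be inflated, or that a mixed model would recover the true change. The documents support neither: they give no dropout rate and do not show that loss will be informative, and step 6 shows where the mixed model fails. Nor is there a basis here for making follow-up or GAF secondary. The plan calls all three visits primary, and that choice is separate from missing data.

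Severity: should-fix for a 30-person pilot.

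**What to change.** Before the data are analysed, amend the statistical section as follows:

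1. Replace the ANOVA with a linear mixed model fitted by REML (SPSS MIXED, categorical Time, unstructured covariance) for HAM-D and for GAF. Name the procedure.
2. Define the analysis population as everyone who started CBT, and use every available score.
3. Report the baseline-to-post-treatment and baseline-to-follow-up changes with 95% confidence intervals and standardised effect sizes.
4. Add a missing-not-at-random sensitivity analysis, for example assuming no change from baseline for those lost. A completer ANOVA may be shown as a supplement. It cannot serve as this sensitivity analysis, because it errs in the same direction as the bias of concern.
5. Report how many participants have a score at each visit and, where known, why the others do not.

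The cost is plan wording and a little more analysis work, with the same software, visits and data. The reported improvement may be somewhat less favourable.

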The two drug administrations will be conducted with one individual participant at a time, each done in a single day. The first drug session (10mg dose) will be conducted over a 6-hour period and the second, high dose session (25mg) will be conducted over an 8-hour period. The first drug administration will be conducted following the third CBT session; the second will be conducted following the sixth session. Participants will be instructed to eat a light, low-fat breakfast on the day of the drug session and to arrive at the study site at 8am.

When the participant arrives at the UCLA Semel Institute for the drug session, prior to the psilocybin's administration, the participant will conduct a urine screen to test for the presence of and illicit drugs and, if the participant is biologically female, to confirm that she is not pregnant. Prior to the psilocybin's administration, participants will also be assessed for recent alcohol use through a breathalyzer test. Participants must have negative toxicology and pregnancy (if applicable) screens as well as no detectable amount of alcohol as measured by the breathalyzer test (i.e., 0.00% BAC) in order to proceed with the drug session. Participants who test positive for any illicit drugs, pregnancy, or alcohol will at any of the study screenings will not be allowed to proceed with the drug session and will be removed from the study. Participants will then be re-oriented to the plan for the day, including that they will be taking psilocybin and remaining in the therapy room for the duration of the drug experience (with the exception of bathroom breaks, as needed). The participant will then be given the psilocybin (10mg [administered in two 5mg capsules] for the first administration; 25mg [administered in one capsule] for the second administration) with a glass of water to begin the drug session. The results of the drug and pregnancy screens, administration of study drug(s), and safety measurements throughout the psilocybin session (see below) will all be catalogued on the study's case report form, which is shown in Appendix I (pg. 25).

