Participants must agree not to take other drugs while taking part in this study unless approved by the study team. Participants must not use illicit drugs and you must report to us the use of any prescribed, over-the-counter, or herbal medications. Subjects who test positive for illicit drugs or alcohol at any of the study screenings will be removed from the study. Psilocybin may interact with antidepressant medications and other serotonergic agents. Therefore, participants cannot proceed past the study screening if they are currently on serotonergic agents. If participants need to start taking a restricted drug during the study, they will not be administered psilocybin but will otherwise remain in the study. Restricted drugs which may interact with psilocybin include:

- **Selective serotonin reuptake inhibitors (SSRIs)**, such as fluoxetine (Prozac), sertraline (Zoloft), paroxetine (Paxil), citalopram (Celexa), and escitalopram (Lexapro), and fluvoxamine,
- **Serotonin and norepinephrine reuptake inhibitors (SNRIs)**, such as venlafaxine (Effexor), desvenlafaxine (Pristiq), duloxetine (Cymbalta), and levomilnacipran (Fetzima),
- **Atypical antidepressants**, such as bupropion (Wellbutrin), mirtazapine (Remeron), trazodone (Oleptro), vortioxetine (Brintellix), vilazodone (Viibryd), and milnacipran (Savella),
- **Tricyclic antidepressants**, such as clomipramine, amitriptyline, imipramine (Tofranil), nortriptyline (Pamelor), desipramine (Norpramin), doxepin, trimipramine (Surmontil), and protriptyline (Vivactil),
- **Monoamine oxidase inhibitors (MAOIs)**, such as Selegiline (Emsam), tranylcypromine (Parnate), phenelzine (Nardil) and isocarboxazid (Marplan),
- **Tetracyclic antidepressants**, such as maprotiline,
- **Serotonin modulators**, such as nefazone (Serzone),
- **Agents that may be associated with serotonin syndrome**, such as lithium, efavirenz (Sustiva), St. John's Wort, and 5-hydroxytryptophan, opioids, buspirone, carbamazepine
- **Agents that may interact with psilocybin metabolism/effects**, such as serotonin antagonists (e.g., cyclobenzaprine, ondansetron), antipsychotics, dopamine antagonists, nicotine, modulators of uridine diphosphate (UDP) or glucuronosyltransferase
- **Agents that may increase the risk of psychotic symptoms**, such as carbidopa-levodopa, dopamine agonists, stimulants, anticholinergics, N-methyl-D-aspartate (NMDAR) antagonists

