Participant Education:

- All participants will be informed of the possible side effects and risks previously mentioned through the informed consent form and discussions with study psychologists and research staff.

Consent Procedures:

- Participants will provide informed consent to screening and all study procedures prior to study entrance.

Participant Monitoring and Removal from the Study:

- The research team will continually assess the participant's health throughout the study and will remove participants from the study if physical or mental deterioration is observed.
- Immediate removal from the study will result if significant adverse reaction to psilocybin or assessment procedure is noted.
- Upon removal of a participant from the study, he or she will be provided with the appropriate follow-up treatment by the study physician.

3. SAFETY MEASURES:

Two drug session monitors will be present for the entire drug session. One of the monitors will be the participant's assigned clinician for the psychotherapy. A second monitor will be present to help with the drug session and ensure that the participant will never be alone if the primary monitor needs to step out (e.g., to use the restroom). Both session monitors will be psychologists and/or psychiatrists. These clinicians will receive didactic training in psychedelic-assisted therapy (PAT; see above). They will also have extensive experience with both mood and psychotic disorders and be experienced in managing acute distress in patients through various

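### Removal wording for deterioration, adverse reactions and drug-day positives conflicts with the rules that stop psilocybin but keep participants, and the plan does not say which governs

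*Combined protocol and SAP*

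**What the plan says.** Two sets of rules cover what happens when something goes wrong after enrolment.

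**Removal wording.** In section 2 (Adequacy of Protection Against Risks), under Participant Monitoring and Removal from the Study, the team "will remove participants from the study if physical or mental deterioration is observed". The next bullet reads "Immediate removal from the study will result if significant adverse reaction to psilocybin or assessment procedure is noted". The General Investigational Plan says that anyone testing positive for illicit drugs, pregnancy or alcohol "will not be allowed to proceed with the drug session and will be removed from the study". The drug and medication restrictions in section 1 repeat this without pregnancy: "Subjects who test positive for illicit drugs or alcohol at any of the study screenings will be removed from the study".

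**Retention wording.** Section 3 (Safety Measures) has a longer part under the same heading as the section 2 bullets. Its list of exclusions, which also applies when one comes to light during the study, includes a positive urine screen for illicit substances (cannabis excepted) and pregnancy. For people on that list who have begun CBT, "they will be retained in the study protocol (but not allowed to participate in forthcoming psilocybin sessions"). An adverse reaction to the first dose leads to withdrawal, yet the person stays in the protocol for as long as possible. After the second dose, "Any participant with an adverse drug reaction to the second psilocybin administration will be offered continued support via the study's outlined CBT protocol". A closing sentence says the team will try to keep people withdrawn from study interventions in the assessments, with their consent. Under worsening or non-response, someone who needs more intensive treatment loses psilocybin but continues CBT and assessments.

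The statistical analysis section counts participants enrolled and retained through treatment, over those consented and screened. It also tracks how many complete the 4-month treatment.

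**The concern.** The same event can draw opposite instructions depending on which page staff open, and no sentence gives one set precedence.

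Safety comes first. Persisting effects are asked about at each CBT session and assessment, for up to 6 months after the first dose and 5 months after the second. The suicide protocol relies on regular contact for at least the first 4 months. Removal in the literal sense ends that contact for those who deteriorated or reacted badly. The section 2 bullets do promise follow-up treatment by the study physician, but that is not the planned monitoring.

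The results come second. Removal for deterioration or adverse reaction is plausibly related to outcome. It would take away post-treatment HAM-D, GAF and CSQ-8 and 3-month HAM-D and GAF from people likely to have done poorly, in a single-group pilot whose purpose is to judge feasibility and estimate effect size. The plan specifies a repeated-measures ANOVA over three time points and names no missing-data method. The feasibility percentage would also depend on which wording was followed.

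**Working it through.** **Side by side, by trigger**

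| Trigger | Removal wording | Retention wording | Conflict? |
|---|---|---|---|
| Illicit-drug positive on a drug day | General Investigational Plan; drug restrictions | Exclusion list and the rule after it: no psilocybin, stays if CBT has begun | Yes, for substances other than cannabis |
| Pregnancy on a drug day | General Investigational Plan | Same list and rule | Yes |
| Significant adverse reaction | Section 2 bullet: immediate removal | Dose 1: kept in protocol. Dose 2: offered continued CBT | Yes |
| Deterioration | Section 2 bullet: removal | Psilocybin stopped, CBT and assessments continue | Yes, but only for worsening that needs more intensive treatment |
| Alcohol positive on a drug day | General Investigational Plan; drug restrictions | None stated | No: both places say removal |

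The first dose follows the third therapy session, so every drug-day test falls after CBT has begun. The retention rule therefore applies to each listed drug-day positive. At entry screening, before CBT, removal is right and there is nothing to reconcile.

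**Which is meant?** Two things point to retention. The Safety Measures text says withdrawn from the study about people it then retains, and its closing sentence speaks of withdrawal from interventions. The drug-restriction text says of someone who must start a restricted drug that "they will not be administered psilocybin but will otherwise remain in the study". That second example also shows that the authors could state the distinction plainly when they chose to.

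**Retention percentage.** One person's weight is 1/(denominator).
- With the planned 30 enrolled: 1/30 = 3.3 percentage points.
- With the plan's own denominator (consented and screened; number not given), assumed here to be 60: 1/60 = 1.7 points.

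These are maxima, since an affected person might not finish treatment under either wording.

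**Scale of possible HAM-D bias.** The documents give no expected change, SD, removal rate or correlation, so every input here except n = 30 is an assumption. Let k of n = 30 people be removed because they rank highest on a trigger that correlates rho with HAM-D change. If they drop out of the analysis, mean improvement is overstated by

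rho × SD × m × k/(n − k),

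where m is the mean of the k largest of n standard normal values (about 1.68 for the top 3 of 30).

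- SD 7, k = 3, rho 0.3: 0.3 × 7 × 1.68 × 3/27 = 0.39 points.
- SD 7, k = 3, rho 0.5: 0.5 × 7 × 1.68 × 3/27 = 0.65 points.
- SD 5 with rho 0.3, to SD 9 with rho 0.5 (k = 3): 0.28 to 0.84 points.
- SD 7, k = 1, rho 0.3 to 0.5: 0.15 to 0.25 points.
- Ceiling, the worst three exactly (rho = 1, SD 7): about 1.3 points.

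The standard error of the mean change would be 7/√30 = 1.28, so the 0.39 to 0.65 range is 0.3 to 0.5 of a standard error. The sum compares full removal with full follow-up. The retention rules promise only an attempt, so the difference attributable to the wording would be smaller.

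**The case against.** The strongest reply is that the specific governs the general. The section 2 bullets are a short summary, and the Safety Measures text under the same heading is the detailed procedure. It addresses adverse reactions and marked worsening directly and explains that withdrawal means withdrawal from interventions. The consent forms may also settle the matter; they were not available. Much of this stands, and it is why retention is the likelier intent. But the text never says that one part elaborates the other, and staff who acted on the section 2 bullets alone would be following the protocol.

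Three stronger readings are tempting and are not supported.

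- *The HAM-D result will be biased because the plan discards those who do badly.* This needs staff to apply the short wording against the detailed rules, and any figure rests on assumed inputs. Some loss could occur under either wording, and the lack of a missing-data method is a separate matter that this rewording would not cure.
- *The alcohol rule is another contradiction.* It is not: both places agree on removal. A route to assessments exists only by inference. The breath test is described as a check on compliance, "Participants will be withdrawn from the protocol if they are noncompliant with the study procedures", and the closing sentence on assessments follows those withdrawal rules. Nor is there a stated reason why a positive breath test would track HAM-D change.
- *Three affected people would turn 30/30 retained into 27/30.* That presumes that someone off psilocybin but still in CBT counts as retained, which the analysis section does not say, and that all three would finish treatment. It also uses a denominator that the plan does not use.

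**Conclusion.** The inconsistency is real for four triggers: drug-day illicit-drug positives, drug-day pregnancy, significant adverse reaction, and worsening that needs more intensive treatment. It should be corrected mainly because, read literally, the removal wording ends safety monitoring and the post-treatment and 3-month assessments for people who worsened or reacted badly. The statistical consequence is secondary. Bias in HAM-D change cannot be quantified from the documents; under the assumed inputs it is below one standard error except at the ceiling, where it about equals one, so it is probably modest. Each affected person moves retention by at most 3.3 points on 30 enrolled, and by less on the plan's own denominator. The conclusion rests on the available text, without the consent forms, and it accepts that retention is probably what the authors intended.

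**What to change.** Reword the section 2 monitoring bullets, the drug-day paragraph of the General Investigational Plan and the drug-restriction sentence. Once CBT has begun, each of these events should mean: *discontinue psilocybin (and CBT if clinically needed); study assessments and adverse-effect monitoring continue unless consent is withdrawn*. This matches the Safety Measures rules. Apply the same wording to a positive drug-day alcohol test for consistency, and check that the consent forms agree.

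In the statistical analysis section, report two percentages: retained through treatment, and received both psilocybin doses. State that someone who stops psilocybin but completes CBT counts in the first and not in the second unless both doses had been given.

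The cost is a few lines of text plus visits that the Safety Measures section already intends. No safety action is weakened, because psilocybin still stops. The effect estimate may look slightly less favourable.
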